Background/Rationale: The AstraZeneca US PRECISION initiative formed an advisor network of scientific and clinical experts and healthcare practitioners (HCP) to develop a point-of-care tool—the Asthma Impairment and Risk Questionnaire™ (AIRQ™)—for the identification of patients at risk for adverse outcomes from uncontrolled asthma. To date, the AIRQ™ has been qualitatively evaluated among patients in an interview setting to ensure that it is understandable and easy to complete and the feasibility of implementing the AIRQ™ into a variety of clinical practices (i.e. allergy, pulmonary and primary care) was evaluated in a pilot program that was well-received by patients and demonstrated the ease of use by clinical staff. A cross-sectional validation study was conducted that demonstrated the validity of the AIRQ™ relative to a composite of Asthma Control Test™ (ACT™) score plus medical-record documented prior-year exacerbations to derive the final AIRQ™ items, scoring and cut points for levels of asthma control (Murphy et al. 2020). The final AIRQ™ consists of 10 yes/no items with the total score used to identify patients at risk for poor asthma outcomes.

This study aims to evaluate the implementation of the AIRQ™, Asthma Checklist, and educational resources (PRECISION program) in clinical practice using telehealth and in-person platforms.

Objectives and Hypotheses:

The primary objective of this study is:

1. To assess the process (ease of use and challenges to HCPs and patients) and potential benefits (ability to capture and take action to remediate previously unrecognized morbidity) of implementing the AIRQ™, Asthma Checklist, and educational resources (PRECISION program) into clinical practice during telehealth and in-person visits.

The secondary objectives of this study are:

1. To assess asthma patients' clinic visit experiences when the AIRQ™, the Asthma Checklist, and educational resources (PRECISION program) are utilized as part of a telehealth or in-person visit with their HCP;

2. To explore change in AIRQ™ scores from the initial visit to follow-up visit(s) (when available).

The following are exploratory objectives:

1 CCI

CCI

CCI

CCI

CCI

CCI

This study is descriptive and there will be no formal hypothesis testing for the primary objective.

Methods:

Study design: This community program intervention study will examine the process of integrating the AIRQ™, Asthma Checklist, and educational resources (PRECISION program) into clinical practice using either in-person or telehealth visits. Providers use of patients' responses to the AIRQ™, Asthma Checklist, and educational resources to guide treatment and asthma work-up and management also will be examined. The study duration is 12-months, with study enrollment lasting nine (9) months for each site (implementation stage), and an additional three (3) months of follow-up to assess the sustainability of using the PRECISION

Observational Study Protocol Form

Version 3.0

Form Doc ID: AZDoc0059948

Parent Doc ID: SOP LDMS_001_00164328

program in clinical practice (sustainability stage). The nine-month implementation stage will allow for the recruitment of approximately 50 patients at each site for an initial study visit, plus the potential for follow-up visit(s). The three-month sustainability stage will allow for sites to continue to implement the PRECISION program in their clinical practice and for sites to describe any continued benefits of using the PRECISION program at their site.

Approximately fifteen (15) to twenty (20) clinical sites will be recruited to participate in this study, categorized into the following three practice clusters: (1) primary care site (e.g., private practice, FQHC; (2) specialty care site (pulmonary, asthma/immunology); and (3) novel sites (e.g., pharmacy, nurse practitioners, nurse educators, prescribers and Non-prescribers, telehealth component of Allergy and Asthma Network). While all sites will be able to conduct both in-person and telehealth visits, sites will aim to conduct a minimum of approximately 25% of their initial patient visit using a telehealth platform. Both platforms (in-person and telehealth) can be used for the follow-up visit(s) for all practice types.

During the clinic visit (telehealth or in-person), HCPs will assess the patients' responses to the AIRQ™ questions, discuss the results with the patient, and use the Assess component of the Asthma Checklist (as appropriate per HCP judgment). Before completing the initial study visit, patients will be asked if they would be willing to complete additional questions and, for those who agree, sites will send them an electronic survey link (via YouGov) which will include the following questionnaires: the Asthma Clinic Experience (ACE) Questionnaire, **CCI** and a Patient

Sociodemographics Questionnaire. If a follow-up visit (telehealth or in-person) is conducted during the follow-up period, the clinical site will administer the AIRQ™ 3-month recall version (regardless of timing of follow-up visit). Sites/HCPs will complete a Clinical Case Report Form (CRF) after the initial visit and after the follow-up visit (if conducted) for each participant. It should be noted that for all visits (initial and follow up), HCPs will be required to review the Assess component of the Asthma Checklist and provide their responses on the CRF; the Adjust and Review components of the Asthma Checklist will be available, along with the other PRECISION resources, on the study website as well, but will not be mandatory to complete. **CCI**

Additionally, Evidera will host a 30-minute conference call with each clinical site for up to four (4) time points (touchpoints) to discuss the implementation of PRECISION tools (i.e., frequency of visits to and the number of PDF views from study website), assess whether sites are meeting their targets for using the telehealth platform, address site questions, and discuss any challenges of implementing the PRECISION program. These meetings will take place at Months 1, 2, 3 (optional), and 6 and will also be used to identify any sites that may benefit from participating in a re-training session. The optional Month 3 touchpoint will be based on whether the site is having any difficulties with the study.

Study Population: Clinic staff will invite patients age ≥ 13 years with HCP-confirmed asthma diagnosis who are presenting for a clinic visit (telehealth or in-person) to complete the AIRQ™ and participant questionnaires. Each site will aim to recruit approximately 50 patients with a total sample size ranging from approximately 750 to 1,500 patients.

Inclusions Criteria:

Patients must meet all of the following criteria to be eligible for enrollment:

1. \geq 13 years of age at the time of enrollment
2. Prior diagnosis of HCP confirmed asthma
3. Able to read, understand, and speak English or Spanish sufficiently to self-complete or be administered the AIRQ™ via telephone, desktop computer, or mobile device (e.g., smartphone, iPad)
4. Provide consent (adults/parents/guardians) and assent (age 13-17 years) to participate in the study

Exclusion Criteria:

Patients meeting any of the following criteria will not be included in the study:

1. Current diagnosis of active COPD or any lower respiratory diagnosis other than asthma.
2. Has a cognitive impairment, hearing difficulty, acute psychopathology, medical condition, or insufficient knowledge of the English or Spanish language that, in the opinion of the investigator, would interfere with his or her ability to agree to participate and/or complete the AIRQ™ or other study questionnaires.

Data Source(s): Approximately fifteen (15) to twenty (20) clinical sites will be selected to implement the AIRQ™, Asthma Checklist, and educational resources (PRECISION program) into clinical practice using telehealth and in-person platforms. The sites will be selected based on the site principal investigator's experience and qualifications, use of a telehealth platform as part of their care practice, the number of asthma patients visiting the clinic via telehealth per week, the diversity of the asthma patients treated by the clinic, the ability of the site to complete the study tasks in the allotted timeframe, and the anticipated unique component(s) used to contribute to the implementation process by the study site. Each site will be responsible for recruiting approximately 50 asthma patients per site.

Exposure(s):

Patients will complete the following measures:

- AIRQ™ 12-month
- AIRQ™ 3-month Recall (as appropriate)
- ACE Questionnaire (for those who agree; initial visit only)
- [REDACTED]
- **CCI** [REDACTED]
- Patient Sociodemographics Questionnaire (for those who agree; initial visit only)

HCPs will complete the following measures:

- Clinical Case Report Form (CRF)
- Follow-up Clinical CRF (if appropriate)
- Clinical Site Touchpoint Questions (via telephone)
- Post-study Survey
- Qualitative Interview
- 12-Month Post-Initial Visit Exacerbation CRF (when applicable)

Outcome(s):

- Qualitative interview responses
- Post-study Survey responses
- Touchpoint findings
- ACE Questionnaire responses
- [REDACTED]
- CCI [REDACTED]
- Relationship between HCP actions (e.g. step up/step down/no change in therapy, referral to specialist, initiation of biologic) based on assessment component of Asthma Checklist and AIRQ™ scores
- AIRQ™ change scores (when available)
- CCI [REDACTED]

Sample Size Estimations: As the primary aim of this study is to assess the process and feasibility of implementing the AIRQ™, Asthma Checklist, and education resources (PRECISION program) using a telehealth or in-person platform, inferential statistics will not be conducted as part of the primary endpoint, and a formal sample size estimation is not applicable. Each site will target approximately 50 patients with asthma. Implementing the AIRQ™, Asthma Checklist, and educational resources (PRECISION program) among approximately 50 patients per site will provide sites with enough experience to provide feedback on the outcomes, barriers, benefits, challenges, ease of implementation, and areas for improvement for future integration as a telehealth platform.

Statistical Analysis: Descriptive statistics (n, frequency, mean, SD) will be used to characterize the sample in terms of sociodemographic and clinical characteristics. The sociodemographic and clinical characteristics will be summarized for the sample overall as well as for each site and cluster. Descriptive statistics (n, frequency, mean, SD) will also be used to summarize the actions of HCPs (e.g., actions accessed/taken, step up/step down/no change in therapy, referral to a specialist, initiation of biologics), results from the HCP's responses on the Post-study Survey, patients' responses to the ACE Questionnaire and the [REDACTED], AIRQ™ scores, CCI [REDACTED]

CCI The relationships between AIRQ™ scores and specific outcomes (e.g., HCP actions taken/accessed, referrals to specialists, initiation of biologics) will be explored. Change in AIRQ™ score between the initial visit and follow-up visit(s) (using the AIRQ™ 3-Month Recall) will be explored when available by site and cluster.

Qualitative interviews will be summarized based on interviewers' notes and transcriptions. Audio-recordings of interviews from clinical site personnel will be referred to as necessary to supplement interviewer notes. The interview results will be summarized in tabular format, with key advantages, and disadvantages grouped. Additionally, findings from the implementation questions discussed during the clinical site touchpoint meetings will be integrated into the findings from the interviews. Facilitators, challenges and barriers, ease of implementation, and areas for improvement will be summarized. **CCI**

CCI

All analyses will be detailed in a Statistical Analysis Plan. Additional exploratory analyses may be performed to further examine specific aspects of available clinical data.

Observational Study Protocol
Study Code D2287L00028 [EVA-26645-03]
Version 2.0
Date June 16, 2022

AMENDMENT HISTORY

Date	Section of study protocol	Amendment or update	Reason
June 16 2022		1	Revision of exploratory outcome 6 and removal of exploratory outcome 7. Update of site sample size maximum limit

MILESTONES

Milestone	Planned end date
Final Protocol	Q1 2021
IRB Study Protocol Approval	Q1 2021
Site Trainings	June 18, 2021
First Site In	February 15, 2021
First Subject In	March 15, 2021
Last Site in	June 15, 2021
Interviews with Site Principal Investigators/Key Staff	Mar 15, 2022
Database Lock	Q2 2022
High-Level Results in Tabular Format	Q3 2022
Final Report	September 26, 2022

1. BACKGROUND AND RATIONALE

1.1 Background

Uncontrolled and severe uncontrolled asthma (SUA) are under-identified and sub-optimally treated. The clinical and economic burden of SUA is disproportionately high, accounting for nearly 40% of asthma-related costs (Moore et al. 2007; Nunes et al. 2017); uncontrolled asthma affects more than 50% of children and adults with asthma. With advances in asthma therapies, an urgent need exists to optimize uncontrolled and SUA recognition and primary care management; and when indicated, referral to qualified specialists.

The AstraZeneca United States (US) PRECISION initiative formed an advisor network of scientific and clinical experts, as well as healthcare practitioners (HCPs), to develop a point-of-care tool—the Asthma Impairment and Risk Questionnaire™ (AIRQ™). This is designed to identify patients living with asthma whose health may be at risk from uncontrolled asthma, and to facilitate shared decision-making between patients and HCPs. The AIRQ™ is intended to be completed by patients before or at their HCP telehealth, or during an in-person clinic visit and includes questions that address medication use, asthma symptoms, exacerbations, hospitalizations, and asthma-related impairment. The final AIRQ™ consists of 10 yes/no items, with the total score and control categories used to identify patients at risk for poor asthma outcomes. All response options are in an easy yes/no format. In addition to the AIRQ™, HCPs are provided with the Asthma Checklist and supplemental educational resources, based on the Global Initiative for Asthma (GINA) guidelines, National Asthma Education and Prevention Program Guidelines (2007; 2020), and key expert reviews on asthma assessment and management to facilitate decision-making and developed by PRECISION Advisors and approved by the AstraZeneca Medical Information and Promotional Regulatory Affairs teams.

The AIRQ™, Asthma Checklist, and educational resources are for use among patients ≥ 12 years old with an asthma diagnosis and are designed for all HCPs to use following provider experience and comfort level. These resources are meant to assist providers in recognizing, evaluating, and optimizing care for patients with uncontrolled or SUA. They are not intended to be treatment directive or diagnostic, but rather to support HCPs in moving toward precision medicine in practice.

1.2 Rationale

To date, the AIRQ™ has been qualitatively evaluated among patients in an interview setting to ensure that it is understandable and easy to complete. The feasibility of implementing the AIRQ™ into a variety of clinical practices (i.e., allergy, pulmonary, and primary care) was evaluated in a pilot program that was well-received by patients and demonstrated the ease of

use by clinical staff. A cross-sectional validation study was conducted to validate the AIRQ™ relative to a composite of the Asthma Control Test™ (ACT™) score, plus medical-record documented prior-year exacerbations to derive the final AIRQ™ items, scoring, and cut points of varying levels of asthma control (Murphy et al. 2020). The final AIRQ™ consists of 10 yes/no items, with the total score and control categories used to identify patients at risk for poor asthma outcomes.

The AIRQ™ performs well in identifying patients who are well controlled vs. not well/very poorly controlled (with receiver operating characteristic [ROC] curves of 0.93 for the 0 to 10 summed score model) and identifies well/not well controlled vs. very poorly controlled asthma (ROC curves of 0.90 for the 0 to 10 summed score model), as reflected by the combined ACT™ score and prior-year exacerbations. The sensitivity of the AIRQ™ is 0.90 for separating well-controlled vs. all others, with a specificity of 0.96 for separating very poorly controlled from all others. A longitudinal study is being conducted to assess the predictive ability of the AIRQ™ as a screening tool for predicting future exacerbations as well as health-related quality of life (HRQoL).

This study aims to evaluate the implementation of the AIRQ™, Asthma Checklist, and educational resources (PRECISION program) into clinical practice using telehealth and in-person platforms.

2. OBJECTIVES AND HYPOTHESES

2.1 Primary Objective & Hypothesis

The primary objective of this study is to assess the process (ease of use and challenges to HCPs and patients) and potential benefits (ability to capture and take action to remediate previously unrecognized morbidity) of implementing the AIRQ™, Asthma Checklist, and educational resources (PRECISION program) into clinical practice during telehealth and in-person visits.

This study is descriptive and there will be no formal hypothesis testing for the primary objective.

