4.1.14 Post-study Survey

All HCPs who participated in at least 10 telehealth or in-person visits will be invited to complete the Post-study Survey (paper form) (Appendix U). The purpose of this survey is to obtain feedback on the implementation of the AIRQ™ within each site's clinical practice (telehealth platform and in-person visit).

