4.1.15 Semi-structured Interview Guide

A semi-structured interview guide (Appendix V) will be used by the interviewer to obtain information from the principal investigator and key clinical site staff (up to three interviews per site) to gain a deeper understanding of the feasibility of implementing the AIRQ™ via telehealth and in-person, as well as sustainability of using the PRECISION program in their clinical practice. The semi-structured interview guide will include an introduction and specific questions/probes designed to facilitate discussion and optimize consistency across interviews. The interview guide will elicit from site personnel the process for implementing the AIRQ™, and recommendations for improving processes related to telehealth and in-person implementation. Also, any specific initiatives that were integrated into various practices will be discussed. Additional unscripted probes may also be used to gain further information or clarification.

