APPENDIX V. SEMI-STRUCTURED INTERVIEW GUIDES

INTERVIEW GUIDE: KEY CLINICAL SITE STAFF

Interviewer: *Before you meet with the participant for the interview, be sure to look over answers from the Post-study Survey and the site's responses from the Site Feasibility Questionnaire about whether the site has indicated any specific initiative to achieve with the AIRQ™ or what made the site unique for participating in this study.*

Part 1. Before the interview begins, be sure to document verbal consent using the script below

Part 2. Below is the discussion guide, it is to be used as a guide only. The actual areas of conversation are fluid and may be discussed at moments different from the order appearing below.

PART 1. KEY CLINICAL SITE STAFF INFORMED VERBAL CONSENT SCRIPT

PART 2. INTERVIEW

INTERVIEW RULES FOR ALL INTERVIEWS

Please feel free to answer honestly. We are interested in your feedback and observations from implementing these tools in your clinical practice over the past several months.

Turn on Recorder and Begin Interview: This is [*interviewee's name*] with participant [*participant ID*] for Study EVA-26645-04 on [*Date*]. I want to confirm that you agree to participate in this interview and that you agree to today's interview being audio recorded. **Is that correct?**

Background

First, I would like to ask you some background questions.

1. What are your key responsibilities at the clinic?
2. What were your key responsibilities for this implementation study?
3. In general, how did your site conduct the patient visit? *Probe: by telehealth platform, by in-person clinic visit.?*
4. In general, how did your site conduct the telehealth visits? *Probe: by telephone, computer, tablet, etc.?*

Now I would like to ask you some questions about the process you used to administer the AIRQ™, the Asthma Checklist, and educational resources (PRECISION program) as part of a patient's telehealth visit for this study.

Process for Telehealth visit with AIRQ™

5. In your own words, how would you describe the process you used to administer the AIRQ™ to patients during a telehealth visit? (*listen for who administered AIRQ™ and how it was administered and process (i.e., as part of initial intake, by HCP, etc.)*)
6. Approximately how long did it take patients to complete just AIRQ™ during a telehealth visit?
7. Did patients have any problems completing the AIRQ™ as part of the telehealth visit?

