1. OBJECTIVES

1.1 Primary Objectives

The goal of this project is to assess the process (ease of use and challenges to health care professionals [HCP] and patients) and potential benefits (ability to capture and take action to remediate previously unrecognized morbidity) of implementing the Asthma Impairment and Risk Questionnaire (AIRQ®), Asthma Checklist, and educational resources (PRECISION program) into clinical practice during telehealth and in-person visits.

This study is descriptive and there will be no formal hypothesis testing for the primary objective.

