4.1.3.3 ACE Questionnaire

The ACE Questionnaire is a self-administered electronic questionnaire that includes eight questions using a four-point Likert scale (strongly agree, agree, disagree, strongly disagree) and one open-ended question regarding additional comments about their visit or the AIRQ®. Patients who agree will be sent this questionnaire via an e-mailed survey link following their initial visit. Patients are asked to think about how completing the AIRQ® as part of their in-person or telehealth visit may have affected their experience when answering the questions.

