visit will also be summarized by visit platform (telehealth vs. in-person), exacerbation history, education level, language, age, sex and NAEPP step level (Table 10b to 10h). In Table 10i, descriptive statistics (mean, SD, median, range) will be used to detail the average number of AIRQs® completed by patients overall and in each practice cluster. In Table 10j, AIRQ® scores from the patient's final follow-up (if more than 1 follow-up AIRQ) will be summarized.

5.1.1 Primary Objective: Assess the Process and Potential Benefits of Implementing the AIRQ™, Asthma Checklist, and Educational Resources (PRECISION Program) into Clinical Practice

This analysis will be conducted on the HCP analysis set of clinicians who completed the post-study survey. Descriptive statistics (n, %) will be used to summarize the proportion of responses for each of the categorical items on the post-study survey (e.g., How would you rate the overall ease of implementing the AIRQ™ into your clinical practice using the telehealth platform?). Descriptive statistics (mean [SD], median, range) will be used to summarize the number of patients treated using the PRECISION program (Table 11). Results will be presented overall and by practice cluster.

Qualitative analyses will be conducted to evaluate the frequency of descriptive free-text responses to open-ended questions on the post study survey (e.g., What features of the PRECISION program do you think could be improved?) (Table 12 series), from the qualitative interviews with key site staff and clinicians (Table 13 series), and from the implementation touchpoint calls with key site staff and clinicians (Table 14 series).

5.1.2 Secondary Objective(s): 1) To Assess Patient Visit Satisfaction When the AIRQ™ Is Initiated as Part of a Telehealth or In-Person visit with Their HCP; 2) To explore change in AIRQ® scores from the initial visit to follow-up visit(s)

To assess patient satisfaction with AIRQ®, descriptive statistics (n, %) will be used to summarize patient responses to the ACE Questionnaire overall and by practice cluster (Table 7a). Scores will also be summarized by visit platform (in-person vs. telehealth), AIRQ® control level, education level, age, exacerbation history, and patient language (Table 7 series).

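### Patient ease of use is part of the primary objective, but all three primary outcomes are reported by providers or site staff, and no coding of patients' own comments is named

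*Protocol*

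**What the plan says.** Both documents put patients inside the primary objective. Protocol 2.1 sets out "to assess the process (ease of use and challenges to HCPs and patients", and SAP 1.1 repeats it: "assess the process (ease of use and challenges to health care professionals [HCP] and patients".

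Section 4.2.1 of each document lists three outcomes for that objective:

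- **Post-study Survey.** Protocol 4.1.14: "All HCPs who participated in at least 10 telehealth or in-person visits will be invited to complete the Post-study Survey (paper form".
- **Qualitative interviews.** Protocol 4.1.15 uses the guide "to obtain information from the principal investigator and key clinical site staff (up to three interviews per site".
- **Touchpoint discussions.** Protocol 4.1.13 puts these questions to the clinical staff on each call.

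SAP 5.1.1 then gives the analysis: "This analysis will be conducted on the HCP analysis set of clinicians who completed the post-study survey". For free text it says "Qualitative analyses will be conducted to evaluate the frequency of descriptive free-text responses to open-ended questions on the post study survey", and it adds the interviews and the touchpoint calls with site staff and clinicians.

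The ACE Questionnaire, which patients answer by e-mailed link, is a secondary outcome. SAP 4.1.3.3 describes eight four-point items and "one open-ended question regarding additional comments about their visit or the" AIRQ.

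**The concern.** When an objective names two groups, each group needs an assigned source of evidence. Here the patient half rests on what staff noticed or remembered.

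Staff are not always placed to notice. Protocol 4.1.2 lets telehealth patients receive the AIRQ ahead of the visit and complete it themselves. Staff then receive the answers, but do not see how hard the form was to open, read or finish. The respondents are also the people who ran the program.

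At stake is the wording of a primary conclusion. The report could state that the program was easy for patients when no measure assigned to that objective comes from a patient.

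**Working it through.** The plan gives no figure to reproduce. The check is a matching of objective, respondent and item.

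**1. Who answers the primary outcomes.** Survey: providers with at least 10 visits. Interviews: the principal investigator and key staff. Touchpoints: clinical staff. Patient-reported: 0 of 3. Protocol 5.1.1 and SAP 5.1.1 name no other source.

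**2. What those instruments ask about patients' difficulty.**

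- Post-study Survey (Protocol Appendix U): items 3 and 4 rate the ease of implementing the AIRQ in the provider's own practice. No item asks whether patients found it easy.
- Clinician interview guide (Appendix V): usefulness, likes and dislikes, and continued use. No item on patient ease.
- Key-staff interview guide (Appendix V): time patients took (items 6 and 10); "Did patients have any problems completing the" AIRQ, for telehealth and in-person visits (items 7 and 11); what patients asked about particular items (7a); and difficulties with the Spanish version (12). SAP Appendix B reports that the AIRQ was given only in English, so item 12 can add little.
- Touchpoint questions (Appendix T): item 6 asks about participant-level factors on each platform.

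Proxy coverage therefore exists, in one of the two interview guides and one touchpoint question. The ceiling on interviews of both kinds is 3 × 15 = 45 to 3 × 20 = 60. The ceiling on touchpoint calls is 4 × 15 = 60 to 4 × 20 = 80. The target sample is 750 to 1,500 patients.

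**3. What the visible patient forms ask.** The eight ACE rating items (Appendix L) cover discussion, information about the condition, information about medicines, test results, reasons for tests, additional care, shared decisions and time with the provider. Item 1 comes closest, but it asks whether the AIRQ helped the discussion, not whether it was easy. Ease-of-use items: 0 of 8. The AIRQ, its 3-month version and the sociodemographics form have none either.

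**4. What happens to the ACE comment box.**

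| Place | Plan for the ACE |
|---|---|
| Protocol 4.2.2 | Descriptive summary by item, for nine items |
| SAP 4.2.2 | Descriptive summary by item for all items; the text then breaks off mid-sentence |
| SAP 5.1 and 5.1.2 | n and %, Table 7 series |
| SAP Appendix A | Individual items described by frequency |
| SAP 5.1.1 (free-text analysis) | ACE comments not named |

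No visible text names qualitative coding of the comments or links them to the primary objective.

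**5. Timing.** SAP section 2 has all participants enrolled by February 2022, and the survey link goes out within 48 hours of the initial visit (Protocol 3.1). The current protocol is dated June 2022 and the SAP September 2023.

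**The case against.** The other side has real points.

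- The objective does not say that patient ease must be patient-reported. Staff may administer the AIRQ by interview, and patients who complete it in advance still give their answers to staff.
- Protocol 1.2 says that earlier patient interviews checked that the AIRQ is understandable and easy to complete.
- Protocol 5.3 justifies the target of about 50 patients per site by the feedback sites can give, and patient experience is a separate secondary objective.
- Eight rating items plus one comment box make nine, so the nine-item summary in Protocol 4.2.2 may include the comments, although Protocol 4.1.9 calls all nine rating questions.
- Part of the patient web survey is redacted, including two patient-completed rows in Protocol Table 1.

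A reader might infer that patients have no voice on ease of use at all, or that their ACE comments will go unanalysed. The documents do not support either. The comment box lets patients raise problems, some summary of it may be intended, and the redacted forms and the cut-off sentence in SAP 4.2.2 cannot be checked.

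What does not stand is the step from there to adequate coverage. The list of primary outcomes is unredacted and assigns no patient measure. A frequency summary under a secondary objective is not a coded source for the primary one. The earlier interviews concerned completing the AIRQ in an interview setting, whereas this objective covers the whole program in routine telehealth and in-person visits.

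**Conclusion.** The point holds as a mismatch between the primary objective and the measures assigned to it. All 3 primary outcomes are reported by providers or staff, 0 of 8 ACE rating items ask about ease of use, and the one visible place where patients can comment on the AIRQ in their own words has no named coding. Patient ease of use is therefore assessed by staff proxy, and the conclusion should say so.

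This rests on the visible text and on reading section 4.2.1 as the complete list of primary outcomes. It makes no claim about the content of the redacted questionnaires. The study is descriptive, so no test or sample size is affected. What changes is what the report may say about patients.

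**What to change.** 1. In SAP 5.1.1, name the ACE free-text comments as a coded patient source for the primary objective. Present them in a patient table beside the Table 12 series, by visit platform and AIRQ administration mode. Both are on the Clinical CRF (Part 3, items 1 and 2), and web-survey responses carry the participant identifier. SAP Appendix B indicates no telehealth visits at the novel site, so the platform split applies to the other clusters. Because data collection is over, record this as a later addition.
2. State beside the table how many patients answered the survey and how many left a comment. Say that the comments are unprompted and come from self-selected responders, in line with the response bias noted in SAP 6.1. They can show kinds of difficulty, not how common each is.
3. Report the survey, interview and touchpoint evidence on patients as staff-perceived ease of use for patients, in both results and conclusion.

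An ease-of-use item for patients beside the ACE would be suitable only if the survey were still open. With enrolment planned to close by February 2022, it is not available for this sample.

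The cost is modest: coding of comments already collected, one further table, and narrower wording.
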